#### 6.2.2.4.2 Intensity of Adverse Events

The intensity of adverse events will be graded according to the NCI-CTCAE scale:

- **Grade 1: Mild;** asymptomatic or mild symptoms; clinical or diagnostic observations only; intervention not indicated.
- **Grade 2: Moderate;** minimal, local, or noninvasive intervention indicated; limiting age-appropriate instrumental Activities of Daily Living (ADL). Instrumental ADL refers to preparing meals, shopping for groceries or clothes, using the telephone, managing money, etc.
- **Grade 3: Severe or medically significant,** but not immediately life-threatening; hospitalization or prolongation of hospitalization indicated; disabling; limiting self-care ADL. Self-care ADL refers to bathing, dressing and undressing, feeding oneself, using the toilet, taking medications, and not being bedridden.
- **Grade 4: Life-threatening consequences;** urgent intervention indicated.
- **Grade 5: Death** (at least possibly) related to the AE.

#### 6.2.2.4.3 Causal Relationship Assessment

The relationship of an AE to the HBI-8000 and pembrolizumab is to be graded by the Investigator as follows:

Definite:

- Distinct temporal relationship with the Study Treatment
- Stops/improves when the Study Treatment has been stopped
- Can reasonably be explained by known characteristics of the Study Treatment

Probable:

- Reasonable temporal sequence from the Study Treatment administration
- Stops/improves when the Study Treatment has been stopped
- Event cannot easily be explained by subject's clinical state or other factors

Possible:

- Reasonable temporal relationship with the Study Treatment
- Event could have been produced by the subject's clinical state or other factors

Unlikely:

- Poor temporal relationship to the Study Treatment

- Subject's clinical state is likely to have an association with the effect

Unrelated:

- Definitely not associated with the Study Treatment administered

Events that are assessed as "definite", "probable" and "possible" in relation to HBI-8000 or pembrolizumab are regarded as AEs that cannot be denied a causal relationship to the Study Treatment and will be handled as "related to HBI-8000 or pembrolizumab" respectively for reporting purposes. Events that are assessed as "unlikely" or "unrelated" to HBI-8000 or pembrolizumab will be handled as "not related to HBI-8000 or pembrolizumab" respectively for reporting purposes.

#### **6.2.2.4.4 Reporting of Adverse Events**

All treatment-emergent adverse events (TEAEs) reported by the subjects, observed during physical examination, vital sign assessment, ECGs and/or review of laboratory test results will be assessed according to NCI CTCAE v.5.0 (CTCAE home page:

<http://evs.nci.nih.gov/ftp1/CTCAE/About.html>

and recorded by severity grades and association with HBI-8000 and pembrolizumab in the eCRF. The reporting of TEAEs should begin at initiation of Study Treatment. Baseline signs and symptoms should also be collected from screening to establish a baseline status for the subjects and will be documented as part of the subject's medical history. The Investigator should complete all the details requested including dates of onset, severity, action taken, outcome, relationship to HBI-8000 or pembrolizumab. Each event should be recorded separately.

Disease progression, signs, symptoms and manifestations of disease progression should not be recorded as an AE. Diagnostic and therapeutic noninvasive and invasive procedures, such as surgery, will not be reported as an AE, but the procedure and/or therapeutic treatment should be recorded on the appropriate eCRF. The medical condition for which the procedure was performed must also be reported.

#### **6.2.2.4.5 Time Period and Frequency for Collecting and Reporting of Serious Adverse Events and Pregnancy Information**

Following the subject's written consent to participate in the study, all SAEs whether related or not related to study drug, must be collected, including those thought to be associated with protocol-specified procedures. An SAE report should be completed for any event where doubt exists regarding its seriousness.

If the Investigator believes that an SAE is not related to study drug but is potentially related to the conditions of the study (such as withdrawal of previous therapy or a complication of a study procedure), the relationship should be specified in the narrative section of the SAE Report Form.

All SAEs must be reported to the Sponsor (or designee) within 24 hours of awareness of the event. All available SAE data, irrespective of the extent of available AE information, must also be recorded in the eCRF within 24 hours of Investigator awareness of the event. In case the eCRF cannot be used by the Investigator to generate the SAE/Pregnancy form, a paper SAE/Pregnancy form will be used and submitted to the Sponsor (or designee). Once the eCRF limitation is

resolved, the Investigator must, as soon as possible, enter all the information from the paper report into the eCRF.

This timeframe also applies to additional new information (i.e., follow-up) on previously forwarded SAE reports. For all SAEs, the Investigator is obligated to pursue and provide information to the Sponsor (or designee). In addition, an Investigator may be requested by the Sponsor (or designee) to obtain specific additional follow-up information in an expedited fashion. In general, this will include a description of the AE in sufficient detail to allow for a complete medical assessment of the case and independent determination of possible causality. Information on other possible causes of the event, such as concomitant medications and illnesses must be provided. In the case of death, a summary of available autopsy findings must be submitted as soon as possible to the Sponsor (or designee). All SAEs requiring expedited regulatory reporting will be evaluated, summarized, and reported to Investigators.

Investigators will be notified by the Sponsor (or designee) of all SAEs that require prompt submission to their IRB or IEC. Investigators should provide written documentation of IRB/IEC notification for each report to the Sponsor (or designee). The Sponsor (or designee) will ensure that all SAEs are reported to the appropriate regulatory authorities.

#### **6.2.2.4.6 Follow-Up of Adverse Events**

Subjects should be asked to specifically describe any signs, symptoms, or AEs (regardless of relationship to Study Treatment) they may notice prior to the start of the study or thereafter. At a minimum, subjects should be asked to report any changes at each visit to the study center. Conditions that the subject experienced prior to informed consent should be recorded in the medical history section of the eCRF.

AEs, Grade 2 and above, considered to be at least possibly related to the Study Treatment must be followed up after the EoT assessment until the events have resolved, returned to the baseline level, are judged by the Investigator to be stable, or no longer require follow up provided the subject is withdrawn from the study due to initiation of new therapy or consent withdrawal for further follow-up. AEs that are assessed by the Investigator as unrelated to Study Treatment will be followed only to the EoT visit. The outcome of any AEs which do not resolve will be recorded as "ongoing" on the eCRF.

Serious adverse events (SAE) and adverse events of special interest (AESI), namely immune-related toxicities, will be collected for up to 90 days following cessation of treatment or 30 days following cessation of treatment if the subject initiates new anticancer therapy, whichever is earlier.

#### **6.2.2.4.7 Clinical Laboratory Evaluations**

Clinical laboratory tests will be reviewed for results of potential clinical significance at all time points throughout the study. The Investigator will evaluate any change in laboratory values. If the Investigator determines a laboratory abnormality to be clinically significant, it is considered a laboratory AE; however, if the abnormal laboratory value is consistent with a current diagnosis, it may be documented accordingly.

Abnormal laboratory test values that are not considered clinically significant by the Investigator will be recorded only on the laboratory section of the eCRF and not in the AE section. However,

abnormal laboratory test results that require Study Treatment modification or other treatment or considered clinically significant by the Investigator are to be recorded in the AE section of the eCRF in addition to the laboratory section. Abnormal laboratory results that meet the definition of an SAE should also be reported on an AE/SAE form. Relationship (i.e., reasonable causal relationship) to HBI-8000 or pembrolizumab and the countermeasures taken will be noted on the eCRF.

#### **6.2.2.4.8 Pregnancy**

If a pregnancy is reported during active treatment of HBI-8000 until EoT, the Investigator must inform the Sponsor within 24 hours of learning of the pregnancy. Protocol-required procedures for study discontinuation and follow-up must be performed on the subject unless contraindicated by pregnancy. Other appropriate pregnancy follow-up procedures should be considered if indicated.

#### **6.2.2.4.9 Overdose**

Overdose is defined as administration to the subject of a dose of test article that exceeds by more than 50 mg/dose or 100 mg/week for HBI-8000, and any dose above the approved 400 mg every 6 weeks or 200 mg every 3 weeks for pembrolizumab. In the case that the overdose did not result in an AE, the Investigator should report this as “overdose, no AE” on the AE/SAE form and specify the intended amount, as well as the actual amount, of drug administered.

All occurrences of overdose must be reported as an AE.

#### **6.2.2.4.10 Deaths**

All adverse events leading to death that occur during the protocol-specified adverse event reporting period, regardless of relationship to Study Treatment, must be recorded on the Adverse Event eCRF and immediately reported to the Sponsor (or designee).

#### **6.2.2.4.11 Other Safety Considerations**

Any significant worsening noted during interim or final physical examinations, electrocardiogram, or any other potential safety assessment required or not required by protocol should also be recorded as a nonserious or serious AE, as appropriate, and reported accordingly.

### **6.3 Safety Monitoring Plan**

Safety oversight is provided by the Sponsor’s internal, Product Safety and Risk Management Committee (PSRMC) that will monitor the study safety data on a periodic basis (frequency of the meeting established by the committee) throughout the study, including review of AEs, adverse events of special interest (AESI) and SAEs.

All enrolled subjects will be evaluated clinically and with clinical laboratory tests during their participation in this study per Schedule of Dosing and Assessments ([Table 1](#)) and as clinically indicated.

Safety evaluations will consist of medical interviews, recording of AEs, physical examinations, and laboratory measurements (hematology, chemistry, virology, and urinalysis).

Subjects will be evaluated for AEs (all grades according to the NCI CTCAE version 5.0), SAEs, and any AEs requiring IP interruption or permanent discontinuation. Subjects who, at time of

progression, have an ongoing AE leading to IP permanent discontinuation will be followed until the event resolves, the Investigator assesses the event as stable, or if the subject is lost to follow-up.

## 7 STATISTICAL CONSIDERATIONS

Statistical analyses will be performed using SAS® v9.4 or higher (SAS Institute, Cary NC, US). Continuous variables will be summarized using descriptive statistics (n, mean, standard deviation, median, minimum, and maximum). Categorical variables will be summarized showing the number and percentage (n, %) of subjects at each category. Time to event variables (i.e., PFS, DoR) will be analyzed using the Kaplan-Meier method. Where confidence limits are appropriate, the confidence level will be 95% (two-sided), unless otherwise stated. Individual data (including relevant derived variables) will be presented by parameter in listings. Results of statistical analyses, descriptive summary statistics and supportive listings will also be presented.

Detailed methodology for summary and statistical analyses of the data collected in this study will be documented in a Statistical Analysis Plan (SAP), which will be finalized and approved before database lock and maintained by the Sponsor. The SAP may modify the plans outlined in the protocol; however, any major modifications will also be reflected in a protocol amendment.

### 7.1 Sample Size Determination

Approximately 20 to 24 subjects are planned to be enrolled to characterize safety and allow for preliminary evaluation of efficacy endpoints in the specific patient population of interest. With a sample size of 20 to 24 subjects the probability that an adverse event with at least a 10% incidence will be detected in at least one subject is high (87.8% to 92.0%) (Table 4). Obtaining this information will help in planning for future immuno-oncology studies.

**Table 4: Probability of Detecting AEs that Occur at Various Frequencies**

True Frequency of AE	Probability of Detecting at Least 1 AE in 20 Subjects (%)	Probability of Detecting at Least 1 AE in 24 Subjects (%)
1%	18.2	21.4
5%	64.2	70.8
10%	87.8	92.0
15%	96.1	98.0
20%	98.9	99.5
25%	99.7	99.9
30%	>99.9	>99.9

### 7.2 Populations for Analyses

The following analysis sets are defined in the study for analyses of safety, efficacy, and pharmacodynamics endpoints.

**Safety Set:** Safety set consists of all enrolled subjects who received at least one dose (any amount) of Study Treatment (HBI-8000).

All safety analyses will be based on Safety Set.

**Full Analysis Set (FAS):** Full analysis set for efficacy consists of all subjects meeting eligibility criteria who receive at least one dose of HBI-8000 in combination with standard of care pembrolizumab, have at least one post-baseline assessment of efficacy, with or without imaging study.

**Per-Protocol Set (PPS):** Per-protocol set for efficacy consists of subjects meeting all eligibility criteria, having received at least 9 doses (75% of 2 cycles) of HBI-8000, with at least 1 imaging study to evaluate disease status after completing 6 weeks (2 cycles) of treatment.

Efficacy endpoints will be analyzed in both FAS and PPS.

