**Statistical methods:**

General:

Statistical analyses will be performed using SAS® v9.4 or higher (SAS Institute, Cary NC, US). Statistical analyses of safety, tolerability and efficacy endpoints will be primarily descriptive in nature. Continuous variables will be summarized using descriptive statistics (n, mean, standard deviation, median, minimum, and maximum). Categorical variables will be summarized with the number and percentage (n, %) of subjects within each category. Time to event variables (i.e., PFS, DoR) will be analyzed using the Kaplan-Meier method. Where confidence limits are appropriate, the confidence level will be 95% (two sided), unless otherwise stated.

All subjects in the safety population (who received any amount of HBI-8000) will be included in the final summaries and listings of the safety data.

Sample Size Estimation:

Approximately 20 to 24 subjects are planned to be enrolled to characterize safety and allow for preliminary evaluation of efficacy endpoints in the specific patient population of interest.

Interim Analysis:

There will be no interim analysis for this Phase 2 study.

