#### **5.6      Dose Modification**

##### **5.6.1      HBI-8000 Administration**

Subjects will take 30 mg of Study Treatment orally approximately 30 minutes after a meal, beginning on Day 1 and continue every 3 to 4 days on the BIW schedule without interruption (e.g., Monday and Thursday, or Monday and Friday repeating every week).

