#### **5.6.2.1.3 Infusion-Related Reactions**

Pembrolizumab can cause severe infusion-related reactions. For severe and life-threatening infusion reactions, pembrolizumab should be discontinued; for mild or moderate infusion reactions the infusion should be interrupted, or the rate of infusion slowed. Immediate access to an Intensive Care Unit or equivalent environment and resuscitation equipment and appropriate medical therapy (including epinephrine, corticosteroids, IV antihistamines, bronchodilators, and oxygen) must be available to treat infusion-related reactions.

All Grade 3 or 4 infusion reactions should be reported within 24 hours to HUYABIO Medical Monitor and reported as a serious adverse event (SAE) if criteria are met. Infusion reactions should be graded according to NCI-CTCAE guidelines.

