## 7.5.2 Safety Analyses

The assessment of safety will include general safety information such as adverse events, vital signs, laboratory tests (hematology, biochemistry, coagulation, urinalysis), concomitant medications, and 12-lead ECGs.

All safety analyses will be conducted using the Safety Population. Descriptive statistics will be used to summarize safety data.

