### 7.5.2.1 Adverse Events

Adverse events will be coded using the MedDRA classification system version 24.0 or higher. The severity of the events will be graded by the Investigator according to the NCI CTCAE version 5.0 or higher.

All adverse events (AEs) will be summarized, and emphasis will be placed on treatment-emergent adverse events (TEAEs). An AE will be considered treatment-emergent if it occurs or worsens in severity from pre-treatment state on or after the first dose date of any study treatment through 30 days after the last dose of any study treatment. All AEs will be listed.

An overall summary of AE will be provided by the frequency and percentage of subjects experiencing an AEs by MedDRA systems organ class (SOC) and preferred term (PT). TEAEs will be summarized by the frequency and percentage of subjects experiencing TEAEs SOC and

PT, and by worst NCI CTCAE severity grade. Summaries will also be provided for treatment related TEAEs, namely, those judged by the Investigator to be at least possibly related to study drug treatment.

Adverse events resulting in discontinuation from treatment or withdrawal from the study, Grade 3 or higher, serious adverse events, and deaths on-study will be tabulated.

All AEs noted during the study will be listed per subject, detailing reported term, system organ class, preferred term, start date, stop date, severity, relationship to each Treatment, TEAE flag, and outcome.

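### The Safety Set requires a dose of HBI-8000, so a subject given only pembrolizumab who has a severe infusion reaction would be left out of the safety tables because of that reaction

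*Combined protocol and SAP*

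**What the plan says.** Section 7.2 defines the set by one drug: "Safety set consists of all enrolled subjects who received at least one dose (any amount) of Study Treatment (HBI-8000". It adds: "All safety analyses will be based on Safety Set". Section 7.5.2 repeats this under another name: "All safety analyses will be conducted using the Safety Population". The synopsis (Statistical methods) agrees on the drug and says that subjects "in the safety population (who received any amount of HBI-8000) will be included in the final summaries and listings" of the safety data.

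Other parts of the protocol treat both drugs as under study:

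- The safety objective (Section 2.2) is the safety and tolerability of the combination.
- The synopsis describes both drugs under Study Treatment, and Table 3 (Section 5.1) lists both as investigational products.
- Causality is graded for each drug (Section 6.2.2.4.3), and exposure is summarised for each (Section 7.4.2).
- Section 7.5.2.1 calls an event treatment-emergent if it occurs or worsens "on or after the first dose date of any study treatment through 30 days after the last dose of any study treatment".

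On timing, Section 5.6.1 has HBI-8000 "beginning on Day 1 and continue every 3 to 4 days on the BIW schedule", and Section 5.6.2 gives the first infusion on Day 1 of Cycle 1. Neither says which comes first. Section 5.6.2.1.3 warns: "Pembrolizumab can cause severe infusion-related reactions".

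**The concern.** Membership of a safety population should not depend on the safety outcome. Here it can. If the infusion comes first and the reaction means that the tablets are never taken, the reaction removes the subject from the denominator and itself from the numerator. The table would then show no severe infusion reaction in a trial where one occurred.

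This matters somewhat more in a trial of this size. Section 7.1 justifies 20 to 24 subjects by the chance of seeing an adverse event in at least one subject. Under that rationale a single event counts, and a rule that can drop a single event from the summaries works against it.

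**Working it through.** **1. The plan's own figure.** Section 7.1 and Table 4 use P(at least one) = 1 − (1 − p)^n. For p = 0.10:

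- n = 20: 1 − 0.9^20 = 87.84%, printed as 87.8%
- n = 24: 1 − 0.9^24 = 92.02%, printed as 92.0%

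Both reproduce. The point concerns definitions and disputes no printed figure.

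**2. One subject followed through the definitions.** Suppose that the infusion is given first on Cycle 1 Day 1, a severe reaction follows, and HBI-8000 is never taken.

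| Question | Source | Answer |
|---|---|---|
| Is the event treatment-emergent? | 7.5.2.1 | Yes, either drug opens the window |
| Is the subject in the Safety Set? | 7.2, synopsis | No, there was no HBI-8000 dose |
| Is the event in a safety summary table? | 7.2, 7.5.2 | No |
| Is it notified? | 5.6.2.1.3, 6.2.2.4.5 | Yes: Grade 3 or 4 goes to the Medical Monitor within 24 hours, and SAEs are collected from consent |
| Is it open to safety committee review? | 6.3 | Yes |
| Is the subject in the disposition table? | 7.3 | Yes, all enrolled subjects are |
| Is the event in the AE listing? | 7.5.2.1, synopsis | Probably |

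The last answer is only probable. Section 7.5.2.1 says "All AEs noted during the study will be listed per subject", whereas the synopsis describes the listings by reference to HBI-8000 recipients without saying that others are excluded. Section 3.1.3 allows consented subjects who did not receive HBI-8000 to be re-consented and re-screened, but gives no analysis rule for one who has already been infused.

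**3. Size if one such subject occurs.** Planned enrolment is 20 to 24. Rates are shown with exact (Clopper-Pearson) 95% limits.

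| Treated with either drug | Reported under 7.2 | Counting either drug |
|---|---|---|
| 20 | 0/19 = 0% (0 to 17.6) | 1/20 = 5.0% (0.1 to 24.9) |
| 24 | 0/23 = 0% (0 to 14.8) | 1/24 = 4.2% (0.1 to 21.1) |

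The smaller denominator matters little. At 10% incidence, the detection probability falls from 87.84% to 86.49% (n = 19) or from 92.02% to 91.14% (n = 23), which is 1.4 and 0.9 points. What matters is the lost event.

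**4. How likely it is.** The documents give no rate for a first-infusion reaction that prevents HBI-8000 from being taken. With assumed rates r, the chance of at least one such subject is 1 − (1 − r)^n:

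| Assumed r | n = 20 | n = 24 |
|---|---|---|
| 0.2% | 3.9% | 4.7% |
| 0.5% | 9.5% | 11.3% |
| 1% | 18.2% | 21.4% |
| 2% | 33.2% | 38.4% |
| 5% | 64.2% | 70.8% |

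The expected number is n × r. Even at 2% this is 0.4 (n = 20) to 0.48 (n = 24), so zero or one subject is the realistic range.

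**The case against.** The strongest defence is that a set of HBI-8000 recipients is a legitimate target. HBI-8000 is the drug being added, and a subject who received only pembrolizumab never received the combination. This stands as a possible deliberate choice. The protocol does not present it as one, however, and gives no other table for subjects who received only pembrolizumab.

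It can also be said that the case needs several steps. The protocol permits the infusion first but does not require it; if HBI-8000 is always taken before the infusion, the case cannot arise. Nor does any section say that an infusion reaction bars HBI-8000. Sections 4.5 and 5.6.2.1.1 let HBI-8000 continue when pembrolizumab stops for reasons other than immune-mediated reactions, although they address continuing rather than starting. A single tablet taken later would bring the subject into the set. All of this stands, and it is why the case is rare.

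A reader might infer three stronger things that the documents do not support:

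- **That the two definitions give one table conflicting denominators.** They do not. The set fixes who is counted and the window fixes which events count. A window wider than the set is workable, and it captures an infusion reaction in a subject who takes HBI-8000 later.
- **That the bias can only flatter the combination.** This is true of the excluded event. But the rule also drops a pembrolizumab-only subject with no event, such as one who withdraws before the first tablet, and that raises other rates. For example, two events would be reported as 2/19 = 10.5% instead of 2/20 = 10.0%.
- **That the event disappears.** It does not: notification, committee review, disposition and probably the listing remain. What is lost is one count in the summary tables.

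**Conclusion.** The point holds as a minor, inexpensive improvement. As worded, the Safety Set permits an exclusion caused by the safety outcome, and no section brings a pembrolizumab-only subject into the safety summaries. If it happens once, a severe infusion-reaction rate of 5.0% (1/20) or 4.2% (1/24) would be tabulated as 0/19 or 0/23.

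This rests on three conditions: the infusion precedes the first HBI-8000 dose, the reaction prevents every later HBI-8000 dose, and the total treated stays at 20 to 24, since no rule for replacing subjects was found. The analyses are descriptive, and no numerical safety stopping rule depends on this rate, so no decision rule in the trial is affected.

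**What to change.** In Section 7.2 and in the synopsis, define the Safety Set as all enrolled subjects who received any amount of HBI-8000 or pembrolizumab on study. The treatment-emergent window in Section 7.5.2.1 then matches the set and can stay as it is. Use one name for the set in Sections 7.2 and 7.5.2, and state that the adverse event listing covers every subject in it.

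Present HBI-8000 duration, compliance, cumulative dose and relative dose intensity (Section 7.4.2), and the summaries of HBI-8000-related events, in the subjects who took HBI-8000.

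If the sponsor prefers to keep a set of HBI-8000 recipients, the alternative is to give that reason and add a table and listing of events in subjects who received only pembrolizumab.

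The cost is a short wording change, best made before the data are reviewed; Section 7 has the SAP finalised before database lock. The one drawback is that a subject with no HBI-8000 exposure may enter the overall safety denominator, which a footnote can make plain. No dosing order or clinical rule needs to change.

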### **4.3.2 Blinding**

This is an open-label study; no blinding procedures will be performed.

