## **6.2 Study Procedures Details**

### **6.2.1 Efficacy Assessments**

The following evaluations will be performed throughout the course of the study:

- Tumor response assessments by physical examination and tumor imaging by CT or magnetic resonance imaging (MRI) according to RECIST v1.1: CT scans are the required modality for measurable disease unless a subject has a clinical condition, e.g. severe contrast allergy, when CT without contrast may be used per institution guidelines. The same scanning modality and the same technique must be used to measure each identified and reported lesion at baseline and throughout the study for a given subject.
- Brain magnetic resonance imaging (MRI) if clinically indicated, and radiographic tumor assessment. If a subject has metal implants, a computerized tomography (CT) scan should be used instead of an MRI.

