### 7.5 Statistical Analyses

#### 7.5.1 Efficacy Analyses

Efficacy analyses will be performed on FAS and PPS. ORR will be estimated based on the proportion of subjects whose best overall response is CR or PR. Disease response will be assessed using RECIST v1.1 as the primary methodology and iRECIST will be used to exclude pseudo-progression when suspected. The estimate of the ORR will be accompanied by a 2-sided

95% exact binomial confidence interval (CI). DCR (CR+PR+SD) will be analyzed similarly. DOR and PFS will be summarized descriptively using Kaplan-Meier methods. The final SAP will provide more details on these analyses.

The efficacy endpoints are the following:

- **Objective Response Rate (ORR)**, defined as the percent of subjects with CR or PR according to RECIST 1.1 and irRECIST criteria, relative to the efficacy population. Subjects who do not have an on-study assessment due to safety issues will be included as non-responders.
- **Disease Control Rate (DCR)**, defined as the percent of subjects with CR, PR or SD according to RECIST 1.1 and iRECIST criteria, relative to the efficacy population.
- **Duration of Response (DoR)**, defined as the time from documentation of tumor response to disease progression.
- **Progression-Free Survival (PFS)**, defined as the time from the start of treatment (Day 1 Cycle 1) until objective tumor progression or death.

The EoT Safety Follow-up visit is scheduled  $30 \pm 3$  days after the last dosing of the HBI-8000 or before the initiation of new cancer treatment, whichever is earlier.

Response rate endpoints (ORR, DCR) will be summarized by number and percentage of subjects meeting the definition of ORR and DCR along with the corresponding exact 95% CI based on binomial distribution.

Time-to-event endpoints (DoR, and PFS) will be summarized by Kaplan-Meier methods (median, 95% CI, number of events, number censored, and Kaplan-Meier figures).

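### The FAS drops treated subjects with no post-baseline assessment, contrary to the plan's own non-responder rule, and neither the ORR denominator nor the primary analysis set is fixed

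*Combined protocol and SAP*

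**What the plan says.** ORR by RECIST 1.1 is the primary objective (Section 2.1), in a single-arm, open-label study of 20 to 24 subjects.

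- **FAS (Section 7.2).** A subject must meet the eligibility criteria, receive at least one dose of HBI-8000 in combination with pembrolizumab, and "have at least one post-baseline assessment of efficacy, with or without imaging study".
- **PPS (Section 7.2).** A subject must meet the eligibility criteria and have at least 9 doses of HBI-8000, "with at least 1 imaging study to evaluate disease status after completing 6 weeks (2 cycles) of treatment".
- **Which set is used (Section 7.2).** "Efficacy endpoints will be analyzed in both FAS and PPS". Neither is called primary.
- **ORR (Section 7.5.1).** It is the "percent of subjects with CR or PR according to RECIST 1.1 and irRECIST criteria, relative to the efficacy population". DCR uses the same denominator. Section 7.2 defines a Safety Set, an FAS and a PPS, but no set called the efficacy population.
- **Missing assessments (Section 7.5.1).** "Subjects who do not have an on-study assessment due to safety issues will be included as non-responders". No other reason for a missing assessment is covered.
- **What counts as an assessment (Section 6.2.1).** The list includes "Tumor response assessments by physical examination and tumor imaging by CT" or MRI, so a clinical examination may be enough to enter the FAS.
- **Timing of the detail (Section 7).** Detailed methods are left to a SAP, "which will be finalized and approved before database lock and maintained by the Sponsor". Section 4.3.2 states: "This is an open-label study; no blinding procedures will be performed".

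**The concern.** The two sections cannot both be followed for a treated subject who has no post-baseline assessment of any kind. Section 7.5.1 counts that subject as a non-responder if the reason was safety. Section 7.2 removes the same subject from both sets in which ORR is calculated. Two programmers working from this text could produce different primary denominators.

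The rule is also too narrow. A subject lost before any assessment through death from disease, clinical deterioration or withdrawal is dropped, and nothing in the plan brings that subject back. These are outcomes that a response rate should count as failures.

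The result of this trial is one proportion with its exact interval. Whom the denominator leaves out therefore bears directly on the primary estimate, and no comparator arm carries the same exclusion. Section 7.1 says the information will help to plan later studies, so an inflated ORR would carry forward. Because the primary set is not named and the study is open label, the choice of headline result could be made after responses are known.

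**Working it through.** **The plan's own figure.** Section 7.1 and Table 4 justify the sample size only by the chance of seeing an adverse event. At 10% true frequency, 1 - 0.9^20 = 87.8% and 1 - 0.9^24 = 92.0%, which agrees with the protocol. There is no target or expected ORR to reproduce, so responder counts below are assumptions.

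**Who is in which denominator.** Take treated, eligible subjects and follow the text literally.

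| Subject's post-baseline data | FAS | PPS | Non-responder rule in 7.5.1 |
|---|---|---|---|
| Imaging after 6 weeks, at least 9 doses | in | in | not needed |
| Clinical examination only, no imaging | in, if an examination counts as an efficacy assessment | out | applies if the reason was safety and the rule means imaging; otherwise nothing is stated |
| Nothing at all, safety reason | out | out | applies, but there is no denominator to enter |
| Nothing at all, other reason | out | out | nothing is stated |

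The last two rows are the defect. The PPS is more selective than the FAS: its dose condition is 9 of 12 doses (2 per week for 6 weeks, 75%), and it also requires imaging after 6 weeks of treatment.

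**Effect on the ORR.** Let N be the number treated, r the responders, and k the treated subjects with no assessment. None of the k can be a responder, so

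ORR(FAS) / ORR(all treated) = [r/(N-k)] / [r/N] = N/(N-k),

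whatever r is, provided r > 0. The same factor applies to DCR.

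- N = 24: 24/23 = 1.04, 24/22 = 1.09, 24/21 = 1.14, 24/20 = 1.20 for k = 1 to 4.
- N = 20: 20/19 = 1.05, 20/18 = 1.11, 20/17 = 1.18, 20/16 = 1.25 for k = 1 to 4.

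**In percentage points**, with assumed responder counts and Clopper-Pearson 95% intervals (the method in Section 7.5.1):

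| k dropped | N = 24, r = 7 | Shift | N = 20, r = 6 | Shift |
|---|---|---|---|---|
| 0 (all treated) | 29.2% (12.6-51.1) | 0 | 30.0% (11.9-54.3) | 0 |
| 1 | 30.4% (13.2-52.9) | +1.3 | 31.6% (12.6-56.6) | +1.6 |
| 2 | 31.8% (13.9-54.9) | +2.7 | 33.3% (13.3-59.0) | +3.3 |
| 3 | 33.3% (14.6-57.0) | +4.2 | 35.3% (14.2-61.7) | +5.3 |
| 4 | 35.0% (15.4-59.2) | +5.8 | 37.5% (15.2-64.6) | +7.5 |

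More responders give a larger shift in points for the same factor. With 10 responders and k = 4, the ORR moves from 50.0% to 62.5% at N = 20 (+12.5) and from 41.7% to 50.0% at N = 24 (+8.3).

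**Against the interval width.** The all-treated intervals are 38.5 points wide (N = 24, r = 7) and 42.4 points wide (N = 20, r = 6). After four exclusions they are 43.8 and 49.4 points wide. The shift is well inside the random error, but the interval does not allow for it.

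**Eligibility condition.** The FAS also removes treated subjects found ineligible. They may or may not respond, so the direction of that effect cannot be stated.

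**The case against.** The best counter-argument is that the clauses can be read together. If the on-study assessment in Section 7.5.1 means the imaging assessment, a subject who stops for toxicity before the first scan but has been examined is in the FAS and counts as a non-responder. On that reading few subjects are lost. Table 1 schedules a physical examination on Day 1 of every cycle, Section 4.4.1 requires an end-of-treatment visit after HBI-8000 is stopped, Section 6.1.4 includes an examination at that visit, and entry requires a life expectancy of at least 12 weeks. Then k is probably 0 or 1, and k = 4 is an upper illustration without support in the documents. This stands as a limit on size. It does not remove the defect: the subject with nothing at all is still in neither set, and reasons other than safety still have no rule.

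Other points also have some force:

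- Section 7.5.1 says efficacy is analysed on FAS and PPS, so the meaning of efficacy population can be guessed. But that gives two denominators, not one.
- Both sets will be reported, so neither result can be suppressed, and Section 7 says major SAP changes will also appear in a protocol amendment. What stays open is which result is presented as primary.
- Section 7.3 tabulates disposition for all enrolled subjects, and individual data are listed, so a reader could rebuild an all-treated ORR. The plan should not leave the primary estimate to the reader.
- The analysis is descriptive, with no threshold or test. No type I error or power is affected; the issue is a biased estimate and interval.
- Sponsor review of each eligibility form (Section 4.3.1) should keep treated but ineligible subjects few, so removing the eligibility condition probably matters little.

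**Conclusion.** The concern holds. As written, Section 7.2 removes from both efficacy sets subjects whom Section 7.5.1 says to count as non-responders, subjects unassessed for other reasons are dropped without a rule, the ORR denominator is not a defined set, and no set is primary.

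The exclusion can only raise the ORR (and the DCR). For one lost subject the shift is 1.3 points (7 of 24) or 1.6 points (6 of 20); for four it is 5.8 or 7.5 points. The factor N/(N-k) is exact. The values of k and r are assumptions, because the documents give neither, and at k = 0 there is no bias. The likely effect is small, but it is on the primary endpoint, in one direction, and cheap to remove. It should be fixed.

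**What to change.** **Section 7.2.** Define the FAS as all subjects who received at least one dose of HBI-8000 in combination with pembrolizumab. This keeps the existing treatment condition and deletes the eligibility and post-baseline-assessment conditions.

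**Section 7.5.1.**

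- Name the FAS as the primary set for ORR and DCR, and put FAS in place of efficacy population in both definitions.
- Replace the safety-only sentence with a rule that every FAS subject without an evaluable post-baseline response assessment, whatever the reason, counts as a non-responder for ORR and as not achieving disease control for DCR.
- Label all PPS analyses as supportive.
- Report the number of FAS subjects without an assessment, by reason.

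Carry the same text into the SAP. The cost is wording only, with no extra data or visits. The reported ORR may be slightly less favourable. If any subject receives HBI-8000 without pembrolizumab, the FAS will be smaller than the Safety Set, and that number should be shown in the disposition table.
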